11.3 Site monitoring

Before study initiation, at a site initiation visit or at an investigator's meeting, a Novartis/delegated CRO representative will review the protocol and data capture requirements (i.e. eCRFs) with the investigators and their staff. During the study, Novartis/sponsor employs several methods of ensuring protocol and GCP compliance and the quality/integrity of the sites' data. The field monitor will visit the site to check the completeness of patient records, the accuracy of data capture / data entry, the adherence to the protocol and to GCP, the progress of enrollment, and to ensure that study treatment is being stored, dispensed, and accounted for according to specifications. Key study personnel must be available to assist the field monitor during these visits. Continuous remote monitoring of each site's data may be performed by a centralized Novartis/delegated CRO organization. Additionally, a central analytics organization may analyze data & identify risks & trends for site operational parameters, and provide reports to Novartis/sponsor clinical teams to assist with trial oversight.

The investigator must maintain source documents for each patient in the study, consisting of case and visit notes (hospital or clinic medical records) containing demographic and medical information, laboratory data and the results of any other tests or assessments. All information on CRFs must be traceable to these source documents in the patient's file. The investigator must also keep the original ICF signed by the patient (a signed copy is given to the patient).

The investigator must give the monitor access to all relevant source documents to confirm their consistency with the data capture and/or data entry. Novartis/sponsor monitoring standards require full verification for the presence of informed consent, adherence to the inclusion/exclusion criteria, documentation of SAEs, and of data that will be used for all primary variables. Additional checks of the consistency of the source data with the CRFs are performed according to the study-specific monitoring plan. No information in source documents about the identity of the patients will be disclosed.

12 Data analysis and statistical methods

The data will be analyzed by Novartis and/or a designated CRO.

The analyses will be conducted on all patient data after data base lock for the trial. Any data analysis carried out independently by the investigator should be submitted to Novartis before publication or presentation.

The primary analyses for all efficacy and safety endpoints will be carried out after the last patient completed Week 24 assessment. [REDACTED]

12.1 Analysis sets

The following analysis sets will be used in this trial:

Randomized Analysis Set (RAS): The RAS is defined as all patients who were randomized. Unless otherwise specified, miss-randomized patients will be excluded from the RAS.

Full Analysis Set (FAS): The FAS comprises all patients to whom study treatment/reference treatment has been assigned by randomization. According to the intent to treat principle,

patients will be analyzed according to the treatment they have been assigned to during the randomization procedure.

Safety Set: The Safety Set includes all patients who received at least one dose of study treatment/reference treatment. Patients will be analyzed according to the study treatment received, where treatment received is defined as the randomized treatment if the patient took at least one dose of that treatment or the first treatment received if the randomized treatment was never received.

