6.1 Study treatment

Investigational treatment – treat-to-target regimen

[figure not shown]
- **Secukinumab 150 mg**, liquid formulation in 1 mL prefilled syringe (PFS) for s.c. injection – all patients will receive 150 mg dose at Baseline, Week 1, 2, 3, 4 and 8. From Week 12, only responders (i.e. patients with ASDAS clinically important improvement, defined as change from Baseline ≥ 1.1) will continue to receive 4-weekly doses until Week 32 if they maintain the response.
- **Secukinumab 300 mg**, liquid formulation in 2 \times 1 mL PFS for s.c. injection – patients who are non-responders at Week 12 will receive 4-weekly doses until Week 20. From Week 24, only responders will continue to receive 4-weekly doses until Week 32.
- **Secukinumab 300 mg as escape treatment**, liquid formulation in 2 \times 1 mL PFS for s.c. injection - patients who were responders at Week 12, but experienced a loss of response (defined as ASDAS change from Baseline < 1.1) at Week 24 will receive 4-weekly 300 mg doses until Week 32.
- **Adalimumab biosimilar (Hyrimoz®) 40 mg**, liquid formulation in 0.8 mL PFS for s.c. injection – patients who are **non-responders to secukinumab 300 mg** at Week 24 will

receive from this time point biweekly doses of adalimumab biosimilar (Hyrimoz®) until Week 34.

Reference treatment – standard-of-care regimen

- Patients will receive treatment according to local practice standards by their treating physician following the current treatment recommendations. Current guideline recommends to start a biological disease modifying anti-rheumatic drug (bDMARD) after the failure of the NSAIDs therapy. According to the 2016 updated Ankylosing SpondyloArthritis International Society (ASAS)/European League Against Rheumatism recommendations, current practice is to start biological therapy with a TNF α blocker. After the failure of the first biologic therapy and in case of positive opinion of the rheumatologist, a switch to another TNF α -inhibitor or to IL-17-inhibitor should be considered ([van der Heijde et al 2017](#)). In accordance with these recommendation the treatment initiation, adjustment and switch will be conducted based on the disease activity and the positive opinion of the investigator. These therapy re-arrangement can be decided and performed at the time of regular study visit (e.g. Visit week 12 or Visit Week 24) or during unscheduled visits as per clinical routine of the investigator.

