12.5.2 Analysis of secondary safety endpoints

For all safety analyses, the Safety Set will be used. All listings and tables will be presented by treatment group.

Safety summaries (tables, figures) will include only data from the on-treatment period with the exception of Baseline data, which will also be summarized where appropriate (e.g. change from Baseline summaries). In addition, a separate summary for death including on-treatment and post-treatment deaths will be provided. In particular, summary tables for AEs will summarize only on-treatment events, with a start date during the on-treatment period (i.e. treatment-emergent AEs as defined below).

The on-treatment period lasts from the date of first administration of study treatment to 30 days after the date of the last actual administration of any study treatment.

Adverse events

All information obtained on AEs will be displayed by treatment group and patient.

The number (and percentage) of patients with treatment-emergent AEs (defined as events started after the first dose of study medication or events present prior to start of study treatment but increased in severity based on PT) will be summarized in the following ways:

- By treatment, primary system organ class and PT.
- By treatment, primary system organ class, PT and maximum severity.
- By treatment, standardized MedDRA query and PT.

Separate summaries will be provided for study medication related AEs, death, SAEs, other significant AEs leading to discontinuation, AEs leading to dose adjustment and AE of special interest.

Adverse events will be summarized by presenting, for each treatment group, the number and percentage of patients having any AE, having an AE in each primary system organ class and having each individual AE (PT). Summaries will also be presented for AEs by severity and for study treatment related AEs. If a patient reported more than one AE with the same PT, the AE with the greatest severity will be presented. If a patient reported more than one AE within the same primary system organ class, the patient will be counted only once with the greatest severity at the system organ class level, where applicable. Serious adverse events will also be summarized.

Vital signs

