2.1.1 General definitions

Study treatment: Study treatment refers to:

1. Investigational treatment Treat to Target (T2T) = secukinumab 150 mg and/or 300 mg and/or adalimumab biosimilar 40 mg (GP2017)
2. Standard of Care (SOC) treatment up to the maximum recommended dose at the discretion of the investigator

The **treatment phase** is defined as the period from randomization until end of the last treatment period with treatment periods defined as:

- Period 1: date of randomization until day before visit Week 12
- Period 2: date of visit Week 12 until day before visit Week 24

- Period 3: date of visit Week 24 until day before visit Week 36

The following exceptions are made to these definitions:

- If visit Week 12 or 24 is missing but the next visit is documented, the visit date is interpolated in the middle between the earlier and the later visit.
- End dates of period 1, 2, 3: If no further visit was performed during the treatment phase after start of the period, the end date is set to the documented end of treatment date or to the period start date, if no treatment was applied in this period.
- End date of period 3: If the documented end of treatment date is on visit Week 36 date or later, the end date of period 3 is set to the end of treatment date.
- Treat-to-Target group: If treatment was not applied at visit Week 12 or 24, or the last dose of the previous period was still applied on the date of visit, the start date of period 2 resp. 3 is set to the date of first dose in this period. Cases where the last dose of the previous period was still applied on the visit date are identified by the same dose as in the previous period applied on the visit date, but treatment was switched at the first dose after the visit.

Treat-to-Target regimen

Starting from Baseline, subject will be treated with secukinumab 150 mg subcutaneous (s.c.) weekly until Week 4 and then at Week 8.

At Week 12

- If the subject achieves and maintains an ASDAS clinically important improvement (i.e. change from Baseline in ASDAS ≥ 1.1 indicating subjects is a responder), then the subject will continue with secukinumab 150 mg s.c. every 4 weeks up to Week 32.
- If the subject did not achieve ASDAS clinically important improvement (i.e. non-responder) then the subject will receive an escalated dose of secukinumab 300 mg s.c. every 4 weeks until Week 20.

At Week 24

Subjects who are receiving secukinumab 300 mg and

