- Achieves ASDAS clinically important improvement (i.e. responder) will continue with secukinumab 300 mg s.c. every 4 weeks up to Week 32.
- Do not achieve ASDAS clinically important improvement (i.e. non-responder), will be switched to adalimumab biosimilar (GP2017) 40 mg s.c. every 2 weeks until Week 34.

Escape arm

- Subjects who are receiving 150 mg secukinumab (i.e. were responders at Week 12) can be escalated at Week 24 to 300 mg secukinumab every 4 weeks until Week 32 if they experience a loss of response, where loss of response is defined as ASDAS change from Baseline <1.1 .

If the ASDAS measurement is missing at a visit, it is assumed that the planned dose continues for the next treatment period.

Standard of Care Regimen

Patients will receive treatment according to local practice standards by their treating physician following the current treatment recommendations with NSAIDs as the first-choice drug treatment and disease-modifying anti-rheumatic drugs (DMARDs) for patients with active disease because of a lack of response, intolerance, or contraindication to NSAIDs ([van der Heijde et al 2017](#)). Patients will be seen every 12 weeks or more often, if clinically indicated up to Week 36; assessment of the outcome parameters will be performed at Week 12, Week 24 and Week 36.

Study treatment (T2T) start and end date: Study treatment start date is defined as the first date of study drug administration and recorded on the Drug Administration Record (DAR) Electronic Case Report Form (eCRF) page. Similarly, study drug end date is defined as the last date of study drug administration and is recorded on the DAR eCRF page.

SOC treatment start and end date: SOC treatment start date is defined as the first date of any SOC drug for AxSPA treatment after randomization. Similarly, SOC drug end date is inferred as the last date of any SOC drug administration for AxSPA treatment within the treatment phase.

Study day: Study Day 1 is defined as the first day of administration of randomized study treatment. Study day will be calculated as (event date – study drug start date + 1 day) for events that occurred on or after study drug start date (e.g. visit, lab samples, AEs). For events prior to study drug start date (e.g. time since diagnosis), study day will be negative and calculated as (event date – study drug start date).

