2.2 Analysis sets

Enrolled Set (ENR): The ENR will comprise all patients, who provided informed consent.

Randomized Analysis Set (RAS): The RAS is defined as all subjects who were randomized. Unless otherwise specified, misrandomized subjects will be excluded from the RAS. Misrandomized patients are defined as cases where subjects were mistakenly randomized by the investigator/qualified site staff either prematurely or inappropriately prior to confirmation of the subject's final randomization eligibility and double-blind treatment was not administered to the subject.

Full Analysis Set (FAS): The FAS comprises all subjects to whom study treatment/reference treatment has been assigned by randomization. According to the intent to treat principle, subjects will be analyzed according to the treatment they have been assigned to during the randomization procedure.

Safety Set: The Safety Set includes all subjects who received at least one dose of study treatment/reference treatment. Subjects will be analyzed according to the study treatment received, where treatment received is defined as the first dose of study/reference treatment.

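### The SOC arm's Safety Set entry and adverse-event window start at the first axSpA drug taken after randomization, while T2T starts at the Baseline injection, so the arms' AE windows are not comparable; the net direction is not fixed.

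*Protocol*

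**What the plan says.** **Set membership.** Protocol 12.1: "The Safety Set includes all patients who received at least one dose of study treatment/reference treatment". SAP 2.2 keeps the at-least-one-dose rule and assigns the arm by treatment received, "where treatment received is defined as the first dose of study/reference treatment".

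**What counts as a dose.** SAP 2.1.1 includes in study treatment "Standard of Care (SOC) treatment up to the maximum recommended dose at the discretion of the investigator".

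**Start of the clock.** In T2T, "Study treatment start date is defined as the first date of study drug administration"; Protocol 6.1 schedules that injection at Baseline. In SOC, "SOC treatment start date is defined as the first date of any SOC drug for AxSPA treatment after randomization". Protocol 6.1 sets no dosing day for SOC and says of starting, adjusting and switching therapy: "These therapy re-arrangement can be decided and performed at the time of regular study visit (e.g. Visit week 12 or Visit Week 24". That sentence goes on to allow unscheduled visits as well.

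**End of the clock.** For SOC, "SOC drug end date is inferred as the last date of any SOC drug administration for AxSPA treatment within the treatment phase". Under SAP 2.1.1 the on-treatment period runs from first administration to the later of 30 days after the last administration and the end of the treatment phase.

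**What is tabulated.** Protocol 12.5.2 describes treatment-emergent events as "defined as events started after the first dose of study medication", or earlier events that worsened. SAP 2.8.1 repeats this with study treatment in place of study medication and restricts AE summary tables to events starting in the on-treatment period.

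**The concern.** The number and percentage of patients with treatment-emergent AEs is the listed endpoint of a secondary objective, and it is tabulated by arm. One nominal rule works differently in the two arms. In T2T, first dose and randomization fall on the same visit. In SOC, the first dose is a post-randomization event that depends on the investigator and on whether the patient was already taking an axSpA drug.

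Patients taking none can be enrolled: Protocol 5.1, criteria 4 and 6, admit patients with NSAID intolerance or contraindication. Such a patient in SOC has no counted AEs until a drug is started. If none is ever started, the patient is in neither numerator nor denominator.

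The SAP does define a treatment phase that begins at randomization in both arms. For AE counting, though, it can only extend the end of the window; it does not set the start or decide Safety Set entry. SAP section 4 lists no change to the protocol's analyses. At stake is whether the two columns of the AE table describe the randomized arms over the same time.

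**Working it through.** No stated figure needs reproducing; the point rests on definitions. Day 1 is randomization.

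**1. Windows**

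- T2T on secukinumab: last dose Week 32 (Protocol 6.1.3) = Day 225; 225 + 30 = **Day 255**.
- T2T switched to the adalimumab biosimilar: last dose Week 34 = Day 239; 239 + 30 = **Day 269**.
- SOC on a daily drug to the end of the treatment phase (day before the Week 36 visit, Day 252): 252 + 30 = **Day 282**.
- SOC with the last drug more than 30 days before the end of the phase: Day 252.

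A SOC start delayed by *d* days gives 282 − *d* counted days on a daily drug. That equals the secukinumab window at *d* = 282 − 255 = 27 days, and the adalimumab window at *d* = 282 − 269 = 13 days.

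**2. What a late start removes**

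Delays of 28, 56 and 84 days remove 33%, 67% and 100% of the first 84 days, and 11%, 22% and 33% of the 252-day phase.

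**3. Early effect (assumed rates)**

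Assume equal constant hazards, 40% with an AE by Week 12, and 25% of SOC starting late. The SOC figure is 0.75 × 40% + 0.25 × [1 − 0.6^((84 − *d*)/84)]. For *d* = 28, 56 and 84 it is **37.2%, 33.9% and 30.0%** instead of 40%. The documents give none of these rates, and the SAP specifies no separate AE table for the first 12 weeks. The figures show only where the loss falls.

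**4. Net effect over the whole window (assumed rates)**

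Assume the same constant hazard in both arms, with 60% over 282 days: λ = −ln(0.4)/282 = 0.00325 per day.

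- T2T, secukinumab: 1 − exp(−255λ) = **56.3%**.
- T2T, adalimumab biosimilar: 1 − exp(−269λ) = 58.3%.
- SOC on a daily drug, on time: 60.0%. Started 84 days late: 1 − exp(−198λ) = 47.4%. Started 28 days late: 1 − exp(−254λ) = 56.2%.

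| Share of SOC starting late | 84 days late | 28 days late |
|---|---|---|
| 10% | 58.7% | 59.6% |
| 20% | 57.5% | 59.2% |
| 50% | 53.7% | 58.1% |

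Five of the six SOC figures are above the secukinumab figure. With an 84-day delay, SOC falls below secukinumab only when the late share exceeds (60.0 − 56.3)/(60.0 − 47.4), about 29%; against the adalimumab window, about 14%. With a 28-day delay the break-even against secukinumab is about 96%.

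**5. Membership (assumed shares)**

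If 5%, 10% or 20% of 150 SOC patients never take an axSpA drug, the SOC Safety Set is about 142, 135 or 120. The percentage moves only if their AE rate differs from that of the others.

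**6. Does moving only the start repair it?**

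No. Under equal hazards SOC would show 60.0% and T2T on secukinumab 56.3%. With both windows cut at Day 252, each arm shows 1 − exp(−252λ) = 55.9%.

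**The case against.** The strongest reply is that few SOC patients should start late, and much of it stands. Protocol 6.7.2 foresees SOC treatment being given at Baseline as well as at Weeks 12 and 24. Protocol 6.1 allows changes at unscheduled visits and cites the recommendation to start a biologic after NSAID failure, and Protocol 4.1.1 has monitors check guideline adherence. Patients who continue a pre-study NSAID plausibly get a start date at or near Day 1. A reader might take the SOC start date to mean the first drug newly started, which would delay the clock for these patients too. The SAP does not exclude that reading, but it pairs the start with the last date of administration, which points to intake. The affected group is therefore mainly patients on no axSpA drug at randomization.

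The consequence is also limited. The safety objective concerns secukinumab's overall safety and tolerability and carries no between-arm test, so neither alpha nor power is touched. AEs are collected from consent (Protocol 10.1.1), SAP 2.8.1 displays AE information by group and subject, and SAP 2.8.2 lists all deaths. What is lost is lost from summary tables and percentages.

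An at-least-one-dose Safety Set is conventional, and calling pre-dose events treatment-emergent strains the term. That argues for keeping drug-specific tables post-dose. It does not justify a between-arm table whose start is fixed by design in one arm and discretionary in the other.

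**Conclusion.** The point holds as a defect of comparability. As written, the rules remove early events from SOC patients on no axSpA drug at randomization, and remove never-treated SOC patients altogether, from the AE summary tables. T2T has no equivalent loss when its first dose is given at Baseline as scheduled.

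A reader might infer that SOC is always observed for less time and that T2T must therefore look worse. The documents do not support that. The start rule lowers the SOC count, but the 30-day tail can lengthen the SOC window by 282 − 255 = 27 days against secukinumab. On the assumed 60% incidence, SOC falls below secukinumab only if more than about 29% start 12 weeks late. The sign depends on the late share, the length of delay and the date of the last SOC drug; the documents give none of these. Nor do they support reading Weeks 12 and 24 as the usual first SOC dates.

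The change is worth making before analysis because it is cheap and the SOC start date is open to two readings. The conclusion that the windows differ needs no assumed rates; every percentage above does.

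**What to change.** Amend Protocol 12.1 and 12.5.2 and SAP 2.1.1, 2.2 and 2.8.1. For the between-arm AE summary:

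- Start the window at randomization in both arms.
- Include all patients randomized to SOC who completed the Baseline visit, with or without a drug.
- Use the same end of window in both arms, for example the end of the treatment phase, and apply its end-of-treatment-date exceptions alike in both.

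Keep the drug-specific AE summaries post-dose. State that a continued pre-study axSpA drug counts from its first intake after randomization.

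The cost is wording plus re-derived start, end and membership flags; no new data are needed. The between-arm SOC column will show post-randomization rather than strictly post-dose events. If the common end is Day 252, T2T events in the tail (Days 253 to 255 on secukinumab, 253 to 269 on the adalimumab biosimilar) leave that table but stay in the drug-specific summaries. T2T membership stays dose-based while SOC membership does not, so a footnote should give the number randomized and never dosed in each arm.

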12.2 Patient demographics and other baseline characteristics

Demographic and other Baseline data including disease characteristics will be listed and summarized descriptively by treatment group and in total for the FAS and Safety Set.

Categorical data will be presented as frequencies and percentages. For continuous data, mean, standard deviation, median, minimum, and maximum will be presented.

Relevant medical histories and current medical conditions at Baseline will be summarized by system organ class and preferred term (PT), and by treatment group.

